### **4. Subject Selection**

We intend on enrolling 30 subjects diagnosed with bipolar disorder, with the goal of randomizing 20 subjects.

Inclusion criteria for this study include: 1) adults between the ages of 18 and 65, 2) diagnosis of bipolar disorder assessed with M.I.N.I. diagnostic interview, 3) currently experiencing symptoms of impulsivity as per BIS total cut-off score equal or greater than 70, 4) if of child-bearing potential must agree to use adequate contraception (e.g. oral contraceptives, intrauterine device, double barrier methods, or total abstinence from intercourse), and 5) vision corrected to normal with contacts/vision does not require glasses or other visual aids.

Exclusion criteria for this study include: 1) currently in depressive, manic, or mixed episode; 2) currently psychotic; 3) judged to be at serious and imminent suicidal risk (C-SSRS $\geq$ 4); 4) currently in alcohol or substance use disorder (meeting criteria in the past 3 months as assessed with M.I.N.I. diagnostic interview); 5) unstable medical conditions; 6) inability to consent or to complete study procedures; 7) failure to meet standard MRI safety requirements (e.g. claustrophobia, non-removable piercings, implanted medical devices, other non-removable metals) as determined by the MRI Safety Checklist; 8) changes in medications or use of augmentative devices and other interventions in the 2 weeks prior to the study; 9) participation in other clinical research trials that may influence primary outcomes or adherence to the proposed study, as assessed by the PI and the Co-Is; and 10) current pregnancy.

Source of subjects will include outpatient clinics at MGH and McLean, the Translational and Clinical Research Center, and Registries/Patient Databases such as the RPDR and Patient Gateway Announcements and or Invitations. We will recruit primarily through referrals from physicians, flyers, online advertisements, and platforms such as Partners Rally and ResearchMatch. We will respond to all individuals who express interest in the study, whether it is from an online recruitment source or through a referral from outpatient clinics at MGH. Clinical research coordinators will primarily handle recruitment and outreach, though some tasks may fall to other members of study staff, like interns. Physicians may send referrals directly to [name], who will forward the information to a CRC to make contact.

We will not discriminate against any group of persons. Based upon the composition of the patient population at MGH and Boston, we anticipate that at least 50% of the participants will be women. The percentage of minority participants is expected to be at least 20%, consistent with previous studies in our lab and at MGH. We expect a roughly equal distribution across sex and ethnicity, as has been previously demonstrated with BD, with the potential for slightly more diagnoses of BD type-I among men and BD type-II among women. Fetuses, children, prisoners, and institutionalized individuals will not be recruited, because they are beyond the scope of the objectives. We will review recruitment regularly at team meetings to track progress and adjust recruitment strategies as needed.

We are only enrolling English-speaking participants in this study since the measures used are developed and validated in the English language and because non-English speaking subjects may not be able to understand study procedures, which could undermine the validity of the results.

## 5. Subject Enrollment

Individuals interested in participating in the study will contact study staff through online recruitment platforms, such as Partners Rally and ResearchMatch. Additionally, patients may be referred to the study from outpatient clinics at MGH. All interested individuals will undergo a screening by trained study staff to ensure eligibility and, importantly, their capacity for voluntary, informed consent. Study staff will describe the study and go through informed consent procedures. Subjects will read the consent form without any time constraints and will be provided the opportunity to ask any questions related to study procedures. Individuals will be officially enrolled upon signing the consent form. This study will not change the clinical care that subjects receive, meaning that all subjects participating in the study will receive the same clinical care as those who are not.

Individuals interested in participating will first be phone-screened for eligibility prior to signing the consent form. The PI and licensed physician co-Investigators with detailed knowledge about the study aims, logistics, procedures, risks, benefits, and alternatives will obtain written informed consent from subjects who meet criteria for this study. Individuals will be given the opportunity to take time to consider participation prior to signing the consent form. Since [name] patients might be offered the participation in this study, the PI, [name], or other licensed co-Is will review the consent and co-sign the consent for any study subjects referred to the study by [name]. This measure will be implemented to prevent any type of coercion.

All subjects participating in the study will receive the same standard of care as those who are not. There are additional study procedures that subjects will undergo, though this should have little to no impact on clinical care. Further, study participation will not impact access to standard of care, meaning that participating in the study will not prohibit subjects from receiving standard treatments for bipolar disorder.

t-PBM is not considered standard of care and is therefore an alternative treatment for bipolar disorder. Standard of care for bipolar disorder includes, but is not limited to, psychotherapy, medications (such as mood stabilizers, anti-depressants, or anti-psychotics), or device-based treatments (such as ECT). Information on standard of care for bipolar disorder will be provided to all subjects. Subjects may continue with their current treatment regimen throughout the study.

The MGH Brain Photobiomodulation Clinic (Director: [name] PhD) has historically served as a resource for subjects enrolled in t-PBM clinical trials who then wish to continue with specialized supervision. Study staff will offer access to the clinic to all subjects upon study completion.

Participants will be compensated \$125 for each of the following visits: Baseline, Treatment 1, Treatment 5, and Follow Up. For each of these visits, the participant receives \$25 for attending the appointment, \$50 for completion of the first gambling task, and \$50 for the completion of the second gambling task. Participants who complete all portions of the study will receive a total of \$500. Subjects who end study procedures prematurely will be compensated for all completed study procedures. Subjects will be mailed a check at the conclusion of their study participation.

While participants will always receive the full \$50 for completing each gambling task, they will be told that their real-world earnings are based on their performance on the gambling task. They will be told that the maximum amount of real-world money that they can earn in each task is \$50. Participants will be told that the better they do on the task, the closer they will get to earning the full \$50, and that their total earnings will be revealed at the final study visit. The purpose of these gambling tasks is to investigate various aspects of behavior, such as impulsivity and decision-making. In order for these tasks to effectively gather accurate data on these behaviors, it is crucial that the participants believe that the amount of money they earn is based on their decisions within the task. Upon completion of all study procedures, participants will be informed that they will receive the full \$50 for each of the eight gambling tasks that they completed.

This deception may result in increased frustration related to performance on the gambling tasks. This deception involves no more than minimal risk to the participants.

If participants do not believe that their compensation is affected by their performance on the gambling tasks, they will not be sufficiently motivated to perform to the best of their ability. The promise of a monetary reward will create a more realistic model of real-world decision making and impulsivity, which are the behaviors that these tasks are designed to measure. This deception is therefore necessary in order to obtain worthwhile data.

This deception will be disclosed by study staff at the end of the follow up visit. Participants will receive a debriefing form explaining the reasoning for a nature of the deception.

## 6. STUDY PROCEDURES

### Study Visits

#### *Contact with potential participants*

Initial contact made with potential research subjects will include only the minimum PHI (name and email). Study staff will obtain written or verbal consent to continue correspondence through unencrypted emails or will send detailed study and PHI information using the “Send Secure” function. Emails not sent using “Send Secure” to participants will contain an automatic email signature alerting them that the email is not encrypted. If participants are uncomfortable receiving information unencrypted, they should alert study staff who will then proceed to communicate securely with the participant. If an individual contacts the study staff by email first, it is implied that email communications are acceptable. Study staff will verify that individuals are comfortable with unencrypted emails and obtain written or verbal consent to proceed with unencrypted email communication.

#### *Pre-Screen*

Prior to enrolling in the study, interested individuals will be contacted by trained study staff for a pre-screening, which can be completed over the phone or via a REDCap link. The trained study staff will review study details and procedures and will ask a series of questions and administer

two questionnaires (the ASRM and the PHQ-9) to assess eligibility for the study. Additionally, study staff will either administer the Barratt Impulsiveness Scale (BIS) over the phone or send interested individuals the REDCap survey link to assess if their impulsivity levels meet our inclusion criteria. Prior to collecting any information, individuals will be asked to provide verbal authorization to write down their responses and will be given the option to not answer questions if they do not wish to do so. Individuals will also be given the opportunity to provide verbal consent regarding unencrypted emails. If the individual is eligible for the study, they will be invited to a screening visit. If the individual is not eligible or decides not to enroll, any information collected during the phone call will be destroyed to protect privacy. If an individual is eligible for the study and enrolls, the information collected during the pre-screening phase will be added to their research file. Individuals will be sent a copy of the consent form for their review via email and the screening visit will be scheduled. Individuals will be reminded not to discuss medical information through unencrypted emails. Individuals will be instructed not to sign the consent form until after they've discussed it with the clinician during the screening visit.

### *Screening*

Subjects will review the consent form with the study clinician (PI or Co-I; MDs) and be given the opportunity to ask questions. Consent will be obtained by a licensed physician investigator. If the screening visit is conducted remotely using Zoom, the consent form will be collected electronically using REDCap following the MGH eConsent Template. Subjects will then receive an electronic copy of the consent form through their provided email which they can download and keep for their records. This is an automatic function of REDCap. If the screening visit is conducted in-person, the consent form may be collected on REDCap or on paper. If the consent form is signed on paper, subjects will receive a paper copy of the consent. Subjects will be considered enrolled in the study once they sign the consent form.

Subjects will be asked a series of questionnaires to assess eligibility for the study, including the Mini International Neuropsychiatric Interview (MINI), and the Columbia Suicide Severity Rating Scale (C-SSRS). Demographic information, concomitant medications and therapies, prior treatment history, and medical history will be collected. Subjects will complete an MRI Screening Form and the MOODS-SR Lifetime. Screening will also include a dipstick toxicology urinalysis and, if applicable, a dipstick pregnancy test. If the subject is eligible, they will be invited to continue to the baseline visit. If not eligible, the subject will not be invited to continue with the study.

### *Baseline Visit*

Adverse events, as well as concomitant medications and therapies, will be collected. Participants will complete the Young Mania Rating Scale (YMRS), the BIS, the BRIEF-A, the I-7, the CAST-IRR, and the SAFTEE. A licensed clinician will administer the C-SSRS and the CGI-S. Skin color will be recorded using the NIS-SCS. Participants will complete two computerized gambling tasks: The Iowa gambling task and the Delgado gambling task. The order of administration of the gambling tasks will be randomized. This appointment will last approximately 90 minutes.

*Treatment 1*

Vitals will be assessed and recorded. The MRI Safety Checklist will be completed and signed before the MRI. Participants will undergo an MRI Scan. While in the scanner, participants will first undergo a structural scan and resting state scan, followed by a functional scan during which the participants will receive a sham t-PBM treatment. This scan will be followed by a pre-stimulation resting-state functional acquisition. At this time, active t-PBM will be administered, immediately followed by a post-stimulation resting state scan. Participants will then complete the Delgado gambling task. A functional sequence will be collected during the administration of the gambling task. Finally, participants will undergo a post-stimulation resting state functional scan. The MRI will last approximately 75 minutes in total.

Participants will know that they are receiving both active and sham treatment, but they will not be told in which order the treatments will be delivered. Participants will complete the PBQ, CAST-IRR, TSRQ, and the Iowa Gambling Task at the conclusion of the visit. Study staff will complete an intervention tracking form.

*Treatments 2-4*

Treatments 2, 3, and 4 should ideally occur once daily during the three days following the first treatment administration. If necessary, this window can be extended so that these three treatment visits occur within ten days of the Baseline/Treatment 1 visit (in this case, the timing of follow up visits will be adjusted accordingly). Adverse events and concomitant medications and therapies will be assessed and recorded at each visit. Participants will complete the TSRQ and CAST-IRR after treatment administration. Study staff will complete an intervention tracking form for each study visit.

*Treatment 5*

Treatment 5 should ideally occur the day after Treatment 4. If necessary, this window can be extended so that this visit occurs within ten days of the Treatment 1 visit (in this case, the timing of follow up visits will be adjusted accordingly). Adverse events, concomitant medications and therapies, and vitals will be assessed and recorded. The MRI Safety Checklist will be completed and signed before the MRI. Participants will complete the MOODS-SR, the BIS, the BRIEF-A, and the I-7.

Participants will undergo an MRI Scan. A structural scan and a pre-stimulation resting state functional scan will be collected first. Active t-PBM will be administered immediately after the resting-state scan, followed by a post-stimulation resting state functional scan. Participants will then complete the Delgado gambling task. A functional sequence will be collected during the gambling task administration. The MRI will last approximately 45 minutes in total.

Participants will complete the SAFTEE, the CAST-IRR, the TSRQ, and the Iowa gambling task after the MRI/t-PBM session. Study staff will complete an intervention tracking form.

*Clinical Check-in Call*

A licensed study clinician will call the participant (phone or video call) approximately 2-3 days after the final treatment session. Adverse events and concomitant medications and therapies will be assessed and recorded. The clinician will administer the C-SSRS and the CGI-S/I. The clinician may use the PHQ-9 and/or ASRM to guide their call with the study participant, though these scales do not need to be completed in full. The purpose of this call is to check in on the general safety and well-being of the participant.

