**4. To test the effect of repeated t-PBM sessions on manic symptoms (MOODS-SR) in subjects with BD**

*Hypothesis:* repeated t-PBM sessions on the R-dlPFC will significantly decrease the total Mood Spectrum-Self Report (MOODS-SR) score at day 5 and follow-up visit relative to baseline. Dimensional improvements will be analyzed as a secondary step.

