#### *Follow Up Visit*

The follow up visit takes place approximately one week after the final treatment session. This visit will be completed in person. Adverse events and concomitant medications and therapies will be assessed and recorded. Participants will complete the MOODS-SR, the BIS, the BRIEF-A, the I-7, the SAFTEE, the Delgado gambling task, and Iowa gambling task. The order of administration of the gambling tasks will be randomized. A licensed clinician will administer the C-SSRS and the CGI-S/I.

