This 161-item self-report scale assesses manic-depressive symptoms. Participants are asked to answer “Yes” or “No” to each question. Subdomains measure Moods, Energy, Cognition, and Rhythmicity. Time frame is either lifetime or the last week, depending on scale used.

*MRI Safety Checklist*

This form identifies risk factors that may make MRI participation unsafe.

*New Immigrant Survey-Skin Color Scale (NIS-SCS)*

The NIS-SCS is an 11-point scale, ranging from zero to 10, with zero representing albinism, or the total absence of color, and 10 representing the darkest possible skin. The ten shades of skin color corresponding to the points 1 to 10 on the Massey and Martin Skin Color Scale are depicted in a chart, with each point represented by a hand, of identical form, but differing in color. The respondent never sees the chart. We gather this data for use as a potential covariate in analyses as skin color can affect absorption of NIR.

*Patient Health Questionnaire (PHQ-9)*

This nine-item self-report measure assesses the presence and severity of depressive symptoms over the past 14 days. This scale will be administered as part of the pre-screening phase.

*Perceived Blinding Questionnaire (PBQ)*

The PBQ is a self-report questionnaire to determine the degree to which the participant believes they are receiving active treatment or sham.

*Prior Treatment Log*

This form captures information regarding prior treatments for bipolar disorder or other mental health concerns.

*Systematic Assessment for Treatment Emergent Events (SAFTEE)*

The SAFTEE is a commonly used instrument originally developed by NIMH and adapted into a self-report instrument. The version of the scale that we plan to use is the same used by the multi-center, NIMH-sponsored CO-MED trial, and it examines in a systematic fashion all possible treatment-emergent side effects and probes specific adverse symptoms, including suicidal thoughts and behaviors, and self-injurious behavior.

*t-PBM Self-Report Questionnaire (TSRQ)*

An open-ended questionnaire focusing on potential inconveniences and discomforts from the t-PBM treatment.

*Young Mania Rating Scale (YMRS)*

This 11-item clinician-rated scale is used to assess the presence and severity of manic symptoms.

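### After baseline, manic symptoms are measured only by self-report: the one clinician-rated mania scale (YMRS) is listed at baseline alone and is not analysed

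*Combined protocol and SAP*

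**What the plan says.** Section 2 states Aim 4 as "To test the effect of repeated t-PBM sessions on manic symptoms (MOODS-SR) in subjects with BD", and its hypothesis is a fall in the MOODS-SR total at day 5 and at follow-up.

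The YMRS appears in the visit schedule once, under Baseline Visit in section 6: "Participants will complete the Young Mania Rating Scale (YMRS), the BIS, the BRIEF-A, the I-7, the CAST-IRR, and the SAFTEE". The next sentence there gives the clinician's tasks separately, as the C-SSRS and CGI-S. The assessment list in section 6 describes the YMRS differently: "This 11-item clinician-rated scale is used to assess the presence and severity of manic symptoms".

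The later contacts in section 6 read as follows.

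- Treatment 5, before the scan: "Participants will complete the MOODS-SR, the BIS, the BRIEF-A, and the I-7".
- Clinical Check-in Call: "The clinician will administer the C-SSRS and the CGI-S/I". The clinician may draw on the PHQ-9 or ASRM, but neither has to be finished.
- Follow Up Visit: "Participants will complete the MOODS-SR, the BIS, the BRIEF-A, the I-7, the SAFTEE, the Delgado gambling task, and Iowa gambling task", and then "A licensed clinician will administer the C-SSRS and the CGI-S/I".

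Section 4 excludes anyone "currently in depressive, manic, or mixed episode". The only symptom minimum for entry is a BIS total of at least 70. Section 9 plans analyses of the gambling tasks, BIS, BRIEF-A, I-7, MOODS-SR, SAFTEE and TSRQ, but not of the YMRS.

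**The concern.** The protocol collects a baseline score on a mania-specific clinician scale and then plans nothing with it. The score sets no eligibility limit, has no later value to be compared with, and enters no analysis.

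Two things are at stake. The first is Aim 4. If MOODS-SR falls, the only mania-related evidence after treatment is what patients report about themselves, on a total that mixes manic and depressive content. No clinician rating of mania can support or contradict it.

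The second is safety. Section 9 hopes to give an initial safety profile in this population. Section 1 describes the stimulation as intended to excite the right dlPFC, and section 7 names insomnia and irritability as possible effects of t-PBM. A rise in manic symptoms is something a reader will want to see measured, and no scheduled clinician rating after baseline measures it specifically.

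**Working it through.** No figure in the plan bears on this point, so the check is to set each contact in section 6 against the measures that could show manic change.

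| Contact | YMRS | Self-report mood scale | Global clinician rating | Non-specific signals |
|---|---|---|---|---|
| Baseline | listed | MOODS-SR Last Week per section 3, but missing from the section 6 list | CGI-S | adverse events, SAFTEE, CAST-IRR |
| Treatment 1 | no | none | none | CAST-IRR |
| Treatments 2 to 4 | no | none | none | adverse events, CAST-IRR |
| Treatment 5 | no | MOODS-SR | none | adverse events, SAFTEE, CAST-IRR |
| Check-in call | no | ASRM, optional | CGI-S/I | adverse events |
| Follow-up | no | MOODS-SR | CGI-S/I | adverse events, SAFTEE |

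**Count.** Contacts after baseline: 5 treatments + 1 call + 1 follow-up = 7. YMRS is listed at 0 of 7, MOODS-SR at 2 of 7 and CGI-S/I at 2 of 7. A change score needs two readings, so the number of patients who can have a YMRS change is 0 of 20.

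**Is another clinician-rated mania scale available?** The assessment list rules out each candidate. The M.I.N.I. is a diagnostic interview, scheduled at screening. CGI-S and CGI-I score overall clinical status. The C-SSRS covers suicidality. ASRM and MOODS-SR are self-report, and CAST-IRR is a self-report of irritability over 24 hours.

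**Does MOODS-SR fill the gap?** Only in part. The protocol describes it as covering manic and depressive symptoms, and the subdomains it names (mood, energy, cognition, rhythmicity) are not labelled by polarity. The Aim 4 hypothesis concerns the total and leaves the dimensions to a secondary step. Section 9 says the scale will be analysed for a fall in impulsivity, which is not how Aim 4 describes it.

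**Which later contact suits a repeat?** MOODS-SR looks back one week. On the ideal daily schedule Treatment 5 falls four days after Treatment 1, so a one-week window reaches about 7 − 4 = 3 days before the first session. Follow-up is about a week after the last session, so its MOODS-SR window falls after treatment. It is also in person, with a licensed clinician attending. A YMRS taken there would stand beside the cleaner of the two MOODS-SR readings.

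**What would a repeat give?** Up to 20 change scores, one per patient with both ratings. As an illustration, assume 20 complete pairs and a paired t-test (two-sided 0.05, 80% power, noncentrality d√n). The detectable standardised change is then about d = 0.66, that is 0.66 × √20 ≈ 2.95. The documents give no standard deviation for YMRS change, so this cannot be put into scale points. It does show why the result should be read descriptively.

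**The case against.** The strongest reply is that the YMRS is not an endpoint. Aim 4 names MOODS-SR, section 3 says that scale is there particularly for hypomanic symptoms, the power statement concerns Aim 1 only, and section 7 says the study is not testing a treatment for bipolar disorder. On this view a repeat YMRS is a preference. That is fair as to weight: the omission does not invalidate the plan. It does not explain why a baseline score is collected with no planned use.

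The second reply is that a repeat would not cure Aim 4. Sham is given only on day 1, every patient then has active sessions, and no blinded rater is described. Patients near the floor on the YMRS also have little room to fall. All of this stands, and it limits what the fix can claim.

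A reader might infer that no scheduled clinician rating exists after baseline. The documents contradict this. CGI-S is rated at baseline and CGI-S/I at the call and at follow-up. Adverse events, SAFTEE and CAST-IRR add further signals, and section 7 tells patients to report symptoms of mania to the study psychiatrist at once. What is absent is a mania-specific clinician rating.

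A reader might also infer that a single baseline YMRS leaves the trial unable to tell no effect from nothing to improve. That does not follow, because a baseline YMRS is the very reading that shows how much there was to improve. The gap is that no such use is planned. Nor do the documents show that patients will sit at the floor. Hypomanic episodes are not in the exclusion list, section 1 describes patients from euthymic to hypomanic, and no score distribution is given.

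**Conclusion.** The point holds in a limited form. After baseline, manic symptoms are measured only by self-report, and the one clinician-rated mania scale yields a change score for 0 of 20 patients. Manic improvement or worsening therefore cannot be shown on a mania-specific clinician rating, although global and non-specific monitoring is in place. The two descriptions of who completes the YMRS disagree, so even the single reading may not be obtained as the instrument is described.

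This rests on the visit lists in section 6 being complete. It is a cheap and worthwhile improvement to a non-primary aim and to safety reporting. It does not make Aim 4 uninterpretable, and it does not touch the larger weakness of that aim, the lack of a sham comparison for the repeated sessions.

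**What to change.** 1. Reconcile the Baseline Visit text with the YMRS entry in the assessment list, so that the baseline YMRS is clinician-administered.
2. Have the licensed clinician who already attends follow-up for the C-SSRS and CGI-S/I repeat the 11-item YMRS there.
3. In section 9, report YMRS change from baseline to follow-up beside MOODS-SR, labelled as supportive and descriptive, for Aim 4 and for safety. State that it is uncontrolled and that the rater is not blinded.
4. Use the baseline YMRS to report how many patients had little or no manic symptomatology to reduce, since entry sets no minimum. Define that category before the data are examined.
5. While editing, reconcile section 3, which places MOODS-SR Last Week at baseline, with the Baseline Visit list, which omits it. Aim 4 needs that reading.

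The cost is a few minutes of clinician and patient time at follow-up, with no new visit, staff or patients. Items 1, 4 and 5 are changes of wording or analysis only.

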## 2. Specific Aims and Objectives

**1. To test the effect of a single t-PBM session on cerebral blood flow (CBF), while irradiating R-dlPFC, in subjects with impulsivity due to BD**

*Hypothesis:* a single t-PBM session on the R-dlPFC will significantly increase BOLD-signal at the R-dlPFC, relative to sham.

**2. To test the effect of repeated t-PBM sessions on CBF, after irradiating R-dlPFC, in subjects with impulsivity due to BD**

*Hypothesis:* repeated t-PBM sessions on the R-dlPFC will significantly increase BOLD-signal at the R-dlPFC at day 5 relative to baseline.

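### As written, day 1 gives everyone sham first and NIR second, so the Aim 1 contrast is also late versus early scan; Section 9 leaves the PSC reference and scaling open

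*Combined protocol and SAP*

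**What the plan says.** Aim 1 (Section 2) expects that "a single t-PBM session on the R-dlPFC will significantly increase BOLD-signal at the R-dlPFC, relative to sham". Section 3 makes the CBF question the primary aim and the only sham-controlled part, and Section 9 powers the study on it.

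Section 6, Treatment 1, sets out the day-1 scan. After a structural and a resting scan (call the rest scan R1), participants go on, "followed by a functional scan during which the participants will receive a sham t-PBM treatment" (S). Then: "This scan will be followed by a pre-stimulation resting-state functional acquisition" (R2). Then: "At this time, active t-PBM will be administered, immediately followed by a post-stimulation resting state scan" (NIR is N, the rest scan R3). The Delgado task follows in the scanner, and then: "Finally, participants will undergo a post-stimulation resting state functional scan" (R4). The whole scan takes about 75 minutes. Participants know they will get both conditions, but "they will not be told in which order the treatments will be delivered".

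On randomization, Section 4 speaks of enrolling 30 "with the goal of randomizing 20 subjects". The only order the document says is randomized is that of the gambling tasks, at baseline and follow-up: "The order of administration of the gambling tasks will be randomized".

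Section 9 lists smoothing and voxelwise z-scoring as preprocessing. It then takes PSC averaged over the ROI, both during and after stimulation, as the Aim 1 outcome, with condition (sham or NIR) as the independent variable. It has no order or period term and names no reference scan.

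**The concern.** If every participant has sham early and NIR late, condition and scan position are the same variable. Drowsiness, habituation, scanner drift or discomfort that builds up in the scanner then enters the NIR-minus-sham difference in full, and no analysis of that difference alone can take it out. It could be read as a t-PBM effect or could hide one. Withholding the order deals with expectancy; it does not change where each condition falls in the session.

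How much of this reaches the outcome depends on how PSC is formed, and Section 9 leaves that open. R2 is the only rest scan after sham and before NIR, so it can serve as the post-sham measure and as the NIR reference. R3 and R4 are both called post-stimulation. It is not stated whether PSC uses the z-scored or the unscaled series. If these choices are made after the data are seen, they are free choices on the primary outcome.

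Two related gaps: Section 6 names a functional run during sham but none during NIR on day 1 or day 5, while Sections 3 and 9 need data during NIR. For Aim 2, NIR is the second stimulation of the session on day 1 and the first on day 5.

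**Working it through.** **1. The plan's own figure.** Section 9 states 80% power at d=0.5, one-tailed alpha 0.05, Wilcoxon signed-rank, and 20 subjects. At n=20 the exact one-sided critical value is W>=150 (P=0.0487). Simulation with normal differences and d=0.5 gives 67%; a paired t-test gives 69.5%. The stated 80% is not reproduced. That is a separate matter; 67% is the baseline used below.

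**2. Size of an order effect.** The document gives no drift size, so 0.1 to 0.3 SD of the paired difference is assumed. In a fixed order the mean paired difference is (t-PBM effect) + (order shift).

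| Order shift (SD) | Rejection, no t-PBM effect | Power, true d=0.5, shift opposed |
|---|---|---|
| 0 | 5% | 67% |
| 0.1 | 11% | 51% |
| 0.2 | 21% | 35% |
| 0.3 | 35% | 21% |

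These shifts are what remains after any referencing.

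**3. What referencing can remove.** Assume equal spacing: R1, S, R2, N, R3, task, R4 at times 0 to 6. The weight on linear drift is:
- unreferenced, N - S: 3 - 1 = 2 intervals;
- *during*, each run against the rest scan before it, (N - R2) - (S - R1): (3 - 2) - (1 - 0) = 0;
- *after*, using R3, (R3 - R2) - (R2 - R1) = R3 - 2×R2 + R1: 4 - 4 + 0 = 0;
- *after*, using R4, R4 - 2×R2 + R1: 6 - 4 + 0 = 2 intervals.

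So own-rest referencing with R3 cancels evenly spaced linear drift. It does not cancel non-linear or uneven drift, and R4 does not cancel even the linear part.

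**4. What referencing costs.** Start from an unreferenced N - S with d=0.5 (67% power) and keep the same raw effect. With independent run noise of SD s, the contrast SDs are:
- unreferenced: √2·s = 1.41s;
- *during*: √4·s = 2.00s, so d = 0.5×1.41/2.00 = 0.35, power 43%;
- *after* (R3): √(1+4+1)·s = 2.45s, so d = 0.5×1.41/2.45 = 0.29, power 33%.

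A constant correlation between runs scales all three SDs equally, so these results hold at any such correlation. Under AR(1) correlation ρ between adjacent runs, the variances (in units of s²) are 2 - 2ρ² (unreferenced), 4 - 2ρ - 4ρ² + 2ρ³ (*during*) and 6 - 8ρ² + 2ρ⁴ (*after*). At ρ=0.8 the SDs are 0.85, 0.93 and 1.30, so *during* has d=0.46 and 61% power, and *after* has d of about 0.33 and 39% power. The range is therefore 43–61% for *during* and 33–39% for *after*; the upper ends depend on the assumed AR(1) model.

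**5. Scaling.** PSC = 100×(signal - reference)/reference. A z-scored series has mean zero. If z-scoring is per run and the reference is a run mean, the denominator is 0. If it is per session, reference values lie around 0 with either sign. Section 9 does not say PSC is taken from the z-scored series, and does not exclude it.

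**The case against.** The strongest defence is that sham-first is sensible. Both conditions fall in one visit with no stated washout, so putting NIR first in half the participants could contaminate their sham run. That stands: counterbalancing within one visit has its own cost, and a fixed order is defensible if acknowledged. The document does not give this reason, however.

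The order may also vary in practice: Section 4 speaks of randomizing, and participants are not told the order. A reader might infer from Section 6 that the word in Section 4 is simply wrong. The document does not settle that. It contains one written sequence and one unexplained word, and the supportable request is to reconcile them.

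A reader might also infer that z-scoring makes PSC impossible to compute. Section 9 lists z-scoring as preprocessing and does not say which series PSC uses, so this is an ambiguity and not a proven error.

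Nor does anything force a rest-scan reference. Sham is delivered during a functional run, so a pre-stimulation segment of the same run could serve, without using R2 twice. Rest-scan referencing buys cancellation of one form of drift at a real loss of power.

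Finally, R3 is the natural *after* scan because it immediately follows NIR, and Section 3 already says BOLD is measured during NIR on both days. Both points are fair; they make these items of wording to settle, not major defects.

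**Conclusion.** The point holds. Followed as written, the day-1 contrast for the primary, powered aim cannot by itself separate a t-PBM effect from an effect of scan position, because the order is the same for everyone and condition is the only factor. The text of Sections 6 and 9 is enough for this; no drift figure is needed.

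The size is not known. The 11%, 21% and 35% rejection rates, and the fall in power from 67% to 51%, 35% or 21%, assume surviving shifts of 0.1 to 0.3 SD and normal differences; the document supports neither the presence nor the direction of such a shift. A reader might conclude that Aim 1 will give a false positive, or that the order must be randomized. Neither follows: drift could be negligible or could work against NIR, and sham-first may be justified by carry-over. What follows is a limit on what the day-1 contrast alone can be said to show, and a need to fix the PSC definition before analysis.

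**What to change.** 1. Reconcile Section 4 with Section 6 on whether sham/NIR order is varied. If it is fixed, correct the word in Section 4, give the reason for sham-first, and word the Aim 1 conclusion as NIR versus sham in fixed order, not attributable to t-PBM on the day-1 contrast alone.
2. In Section 9, state that PSC is computed from unscaled data. Before analysis, fix one reference for each condition: either a pre-stimulation segment of the same run, or the rest scan immediately before it (R1 for sham, R2 for NIR). Name R3 as the *after* scan and report *during* and *after* separately. If rest scans are the reference, state that R2 enters the *after* contrast twice, that only evenly spaced linear drift cancels, and that power falls as in step 4 of the working.
3. Optionally, add day-1 sham versus day-5 NIR as a supportive sensitivity analysis; each is the first stimulation of its session. State that it carries a session effect and follows four earlier NIR sessions, so it is not the single-session question of Aim 1. A session effect of 0.1, 0.2 or 0.3 SD would again reject in 11%, 21% or 35%.
4. Reconcile Section 6 (Treatments 1 and 5) with Sections 3 and 9 on the functional run during NIR, and note for Aim 2 that NIR is the second stimulation on day 1 and the first on day 5.

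The cost is a few sentences and, if item 3 is taken up, one more analysis of scans already planned, provided the day-5 run during NIR is acquired. No visits or participants are added. The Aim 1 claim becomes more cautious, and rest-scan referencing, if chosen, costs precision.
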